**Selection Criteria:**

*Inclusion Criteria:*

Healthy subjects of Skin Type I-VI females.

Subjects must be between 18 and 74 years of age, and must have visible melasma on the face.

Subjects must read, understand, and sign the Informed Consent.

Subjects must be willing and able to comply with all follow-up requirements.

*Exclusion Criteria:*

Subjects must not have active or localized or systemic infections.

Subjects must not be immunocompromised.

Subjects must not have a coagulation disorder, and must not be using anticoagulation medications.

Subjects must not have history of surgical or cosmetic treatment, including prior skin lightening agents, microneedling or microdermabrasion, or laser or light-based therapies, to the planned treatment areas in the prior six weeks.

Subjects must not have photosensitivity or allergy.

Subjects must not be mentally incompetent.

Subjects must not be pregnant or breastfeeding.

History of skin cancer or pre-cancerous lesions in the treatment area

Subjects must not be currently using aspirin or antioxidants.

Subjects must not refuse to sign the Informed Consent document and/or refuse to comply with all follow-up requirements.

Subjects must never have had gold therapy.

Subjects must never have had radiation therapy to the face. Recent or current suntan or sunburn within 2 weeks.

Clinically dysplastic nevi in the treatment area.

Subjects must not have had collagen, other methods of tissue augmentation, botox, chemical peels, dermabrasion, or resurfacing within the last year.

Oral retinoid (Accutane or Soriatane) or photosensitizing drugs, e.g. Declomycin®, a tetracycline with light absorption in the range of 400 to 450 nm use within 24 months of study entry.

Topical retinoid therapy on neck and/or chest within one month of study entry.

History of keloids or hypertrophic scars

A history of cutaneous photosensitization, porphyria, hypersensitivity to porphyrins, or photodermatitis.

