We hypothesize that addition of 1927-nm fractional low-powered diode laser therapy to topical 5% cysteamine will result in significantly greater improvement in both the clinical appearance of melasma as well as patient satisfaction, compared to topical cysteamine alone. Specifically, we hypothesize:

- 1) Patients will experience improvement in their melasma on both treated sides, with greater improvement noted with combined topical and 1927-nm fractional low-powered diode laser treatment noted on their mMASI scores at weeks 4, 8 and 12.
- 2) Patients will report improvement in satisfaction on patient questionnaires on both treated sides, however there will be greater change in satisfaction noted with combined topical and 1927-nm fractional low-powered diode laser treatment at week 12 compared to baseline (week 0)

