**Objectives:**

- A. To evaluate the efficacy of the Clear & Brilliant Permea laser system in combination with topical cysteamine
  - a. To assess for improvement of melasma after completion of three treatments as determined by the treating clinician and objective measures
  - b. To evaluate subject's satisfaction with melasma treatment and assessment of improvement after three treatments
  - c. To evaluate the length of treatment.
- B. To evaluate the safety of melasma treatment in all skin types using the Clear & Brilliant Permea laser in combination with topical cysteamine
  - a. To evaluate the immediate response to treatment
  - b. To evaluate the subject's assessment of comfort associated with treatments
  - c. To determine the rate of adverse events for the treatment group as a whole

**Study Design:** Single Center, Prospective, With Before-After Analysis

**Study population:** Twenty healthy male or female patients, 18-74 years of age, of all skin types with melasma on the face that wish to be treated. Each subject will receive topical cysteamine cream which they will be instructed to use once a day at home. In addition, one side of the face will be randomly selected for treatment with laser. Patients will receive three monthly treatments, at 4-6 week intervals, on the selected side of the face with the Clear & Brilliant Permea laser. The treatment duration including pre and post treatment procedures is estimated to be 90 minutes per subject. Subjects will return for a follow-up visit 3 months after the initial treatment for a total of four visits. The treatment plan will be the same regardless of the subject's skin type. Four passes, at high setting will be performed.

During the first and fourth visit, the areas of treatment will be photographed with a digital camera under controlled conditions. Subject improvement will be assessed via investigator and subject grading at visit 1 and 4. Improvement in melasma will be assessed by blinded evaluators who will review pre and post treatment photographs taken with VISIA® Skin Analysis System for facial imaging (Canfield Scientific Inc) from visit 1 and 4. Side effects (including pain, redness, dryness, and hyperpigmentation) will be assessed and recorded at visits 2, 3, 4.

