### **Sample size justification:**

#### Statistical Hypothesis:

Null hypothesis: Treatment of melasma on face with Clear & Brilliant laser and topical cysteamine will not lead to significant improvement

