#### Sample Size Calculation:

A sample size is calculated to test the null hypothesis with a one-sided paired t-test for simplicity, although the final analysis may employ a statistically more powerful model.

We calculate that for a two-sided alpha level of 5%, a sample size of 20 subjects will enable us to test the null hypothesis with 80% power. In order to enable the analysis and take into account the potential for dropout we may include up to 25 patients.

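### Eligibility does not require melasma on both sides of the face, so one-sided cases may enter and dilute the split-face comparison

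*Protocol*

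**What the plan says.** - **Eligibility.** Under Selection Criteria in the protocol, subjects "must have visible melasma on the face". The Study population paragraph repeats this without a side requirement: patients "of all skin types with melasma on the face that wish to be treated". Nowhere does the protocol ask for disease on both sides, for comparable sides or for a minimum score per side. The severity classification (mild, moderate, severe) applies to the subject, not to the side.
- **Allocation.** Every subject uses cysteamine, and "one side of the face will be randomly selected for treatment with laser".
- **Question asked.** The primary objective, in the Background, is the combination against cysteamine alone. The first specific hypothesis there reads: "Patients will experience improvement in their melasma on both treated sides, with greater improvement noted with combined topical" treatment and laser.
- **Sample size.** The Sample Size Calculation names a "one-sided paired t-test for simplicity", then a two-sided 5% level, and states that "a sample size of 20 subjects will enable us to test the null hypothesis with 80% power". It gives no effect size, standard deviation or within-patient correlation.
- **Score.** The mMASI table defines a whole-face total from 0 to 24. The malar areas are scored left and right, but forehead and chin are each scored once.

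**The concern.** A split-face comparison presupposes disease on both halves. In a patient with one-sided melasma, the clear half scores zero and cannot improve. If the laser falls on the affected half, the difference between sides is the whole cysteamine effect plus the laser effect. If it falls on the clear half, the difference is minus the cysteamine effect. Neither result isolates what the laser adds.

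The stake is precision. With 20 to 25 patients there is little room for pairs that carry reduced information about the primary question. Eligibility is fixed in the protocol, and an analysis plan could not supply the missing disease on the second side.

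**Working it through.** **1. What 20 subjects and 80% power imply.** Because the protocol gives no effect size or SD, the figure of 20 cannot be reproduced, only inverted. For a paired t-test with n = 20 and two-sided 5%, the critical value on 19 degrees of freedom is 2.093 and the noncentrality is d√20. Solving for 80% power gives d = 0.66, where d is the mean paired difference in units of its SD. The one-sided reading gives 0.58. The steps below use 0.66, on the assumption that the pair is laser side against cysteamine-only side.

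**2. What a one-sided patient contributes.** Let c be the improvement from cysteamine alone, in SDs of the paired difference, and d the added laser effect. The expected difference is c + d or −c, each with probability 1/2:

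- mean = ½(c + d) + ½(−c) = d/2
- mean square, before noise = ½[(c + d)² + c²]

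So the cysteamine term cancels on average but adds spread, and half the laser effect is lost.

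**3. The mixture.** If a share u of patients is one-sided and v is the noise variance of their difference (1 for a two-sided patient):

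- mean = (1 − u/2)d
- mean square = (1 − u)(1 + d²) + u{v + ½[(c + d)² + c²]}
- SD = √(mean square − mean²)

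Two values of v bracket the case. v = 1 gives one-sided pairs the same noise as two diseased sides. v = 0.5 counts noise from the diseased side only, taking sides as independent.

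**4. Worked example: u = 10%, c = 1, v = 0.5.**

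- mean = 0.95 × 0.660 = 0.627
- mean square = 0.9 × 1.436 + 0.1 × (0.5 + ½[1.660² + 1²]) = 1.293 + 0.238 = 1.530
- SD = √(1.530 − 0.394) = 1.066
- standardised difference = 0.627 / 1.066 = 0.588, so power at n = 20 is about 70%

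**5. Range, by simulation of the t-test.** Power at n = 20, two-sided 5%; first figure v = 0.5, second v = 1.

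| Cysteamine effect c | 5% one-sided | 10% | 20% |
|---|---|---|---|
| 0 | 79%, 77% | 77%, 75% | 74%, 70% |
| 0.5 SD | 77%, 76% | 75%, 73% | 69%, 65% |
| 1 SD | 75%, 74% | 70%, 69% | 60%, 58% |
| 2 SD | 69%, 68% | 59%, 58% | 44%, 43% |

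The row c = 0 shows mainly the dilution of the mean. There the SD hardly moves: at 10% it is 0.985 with v = 0.5 and 1.01 with v = 1. From c = 0.5 upwards the SD rises under both choices. At a 1% share and c = 1, power is about 79%.

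With v = 0.5 and c = 1, restoring 80% power would take 23, 25 and 31 evaluable patients at shares of 5%, 10% and 20%. The ceiling of 25 enrolled is already meant for dropout.

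**The case against.** **One-sided cases may never appear.** The protocol does not say that any are expected, and the hypotheses speak of improvement on both sides. At visit 1 the side to be lasered is examined and mapped and melasma is graded, so a clear laser side would probably be noticed. This stands as a limit on the size of the point. It does not close the gap: noticing a clear side is not an exclusion rule, and the visit list includes no check that the other side has disease.

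**The pairing is intact.** A reader might infer that one-sided patients break the pairing or bias the result. They do neither. Both halves still belong to one patient, and randomising the side removes systematic bias in favour of either treatment. A chance imbalance in which side is lasered is ordinary sampling error, already counted in the variance above. What is lost is comparability within the affected pairs.

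**The sample size may not rest on side-to-side pairing.** The design is labelled "Single Center, Prospective, With Before-After Analysis", and the null hypothesis says only that "Clear & Brilliant laser and topical cysteamine will not lead to significant improvement", with no cysteamine-only side named. This objection stands: the documents do not establish which pair the 20 subjects were sized for, so the power figures are an illustration under one reading. The sidedness conflict in that section is a separate matter. The primary objective is nevertheless side against side. Even on a before-after reading of the laser side, a patient lasered on a clear side could show no improvement.

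**Conclusion.** The point holds as a gap in eligibility. The criterion admits patients with one-sided melasma, and the comparison the trial exists to make needs disease on both sides. Each such patient would contribute on average half the laser effect, with extra spread if cysteamine works.

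The size is conditional. On a two-sided, side-against-side reading of the sample size and a cysteamine effect of 1 SD, power would fall from 80% to about 74–75%, 69–70% or 58–60% at one-sided shares of 5%, 10% or 20%. The protocol gives neither the share nor the cysteamine effect.

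A reader might conclude outright that the stated 80% power is not delivered. The documents do not support that, since they do not show that any one-sided patient will enter, and with few of them the loss is near zero. The change is worth making because it is cheap and the sample is small.

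**What to change.** Change the inclusion criterion to visible melasma on both sides of the face. Confirm it at visit 1 by grading each side before the laser side is randomised, and require a per-side mMASI above zero on each side. The mMASI table must then state how the forehead and chin are divided between the sides, because only the malar areas are scored separately now.

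The cost is slightly narrower recruitment, as any patients with one-sided disease are turned away, and the work of defining and recording a per-side score. The split-face comparison needs that score in any case.

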## Protocol Summary

**Study Device:** Clear & Brilliant Touch

**Protocol Number:** XXXXXXXX

**Projected Study period:** Initiation Date: November 2022 Completion Date: November 2023

**Study Duration:** 12 months

**Purpose:** To evaluate the efficacy and safety of the combination 1927nm Low-Powered Diode laser and topical cysteamine cream for treatment of melasma on the face.

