### Procedure:

#### Visit 1 (Screening and Initial Treatment Visit)

- Verify that subject is qualified to participate in the study.
- Ask subject to give personal information, such as name, date of birth, race and ethnicity.
- Review medical and dermatology (skin) history, including history of previous treatments to area being treated.
- Review past and current medications and skin care products.
- See how tall subject is and how much subject weighs
- If subject is a woman and can have children, urine will be tested to see if subject is pregnant. The study doctor or study staff will tell subject if pregnancy test results are positive. The results of the pregnancy testing must be negative in order for subject to be in the study.
- Supply patient with topical cysteamine cream and review instructions for its use
- Identify and examine the area (i.e, side) of face to which the Diode 1927 nm laser will be used (mapping)
- Take photos of face
- Perform grading of melasma
- Perform treatment according to guidelines stated in protocol
- Schedule the next study visit

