#### **Background:**

Melasma is a commonly acquired hyperpigmentary condition characterized by brown spots on sun exposed areas of the face. Treatment of melasma can be challenging as many patients are refractory to therapy, while others experience a chronic or relapsing course. Melasma also significantly impact patients' quality of life with many reporting feelings of frustration, embarrassment, and depression related to their condition. Mainstay of treatment includes topical skin-lightening and brightening agents such as hydroquinone, tranexamic acid, retinoids, azelaic, kojic and ascorbic acids, as well as various chemical peels, laser and light-based therapies. Current gold standard is a triple combination cream consisting of topical hydroquinone, tretinoin, and fluocinolone, along with broad-spectrum sunscreen. However, use of topical hydroquinone is associated with adverse events including irritation and a paradoxical exogenous ochronosis with prolonged use, making its use challenging. Hence, for this difficult, and often recalcitrant disease, additional therapeutic options are needed.

Topical cysteamine is safe, generally well tolerated, and can be used continuously without treatment holidays. Multiple studies have demonstrated its efficacy in the treatment of melasma, including two double-blind, randomized, and placebo controlled clinical trials. Combination therapy of lasers with lightening agents have been shown to augment melasma treatment. However, data on combination laser and topical cysteamine is sparse, and no controlled or split-faced studies have been published. Thus, we aim to investigate combined topical cysteamine with laser, compared with topical cysteamine alone to assess whether this adjuvant therapy can improve the efficacy of cysteamine in the treatment of melasma.

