**Risk Management:**

Subjects will be followed closely during the course of the trial and will have access to the investigators at all times via provision of after-hours telephone and/or pager numbers.

Any investigators, subjects or others present in the room while the laser treatment is rendered will wear suitable eye protection. A local anesthetic may be given before treatment to minimize pain and/or discomfort resulting from laser treatment. All other known risks will be disclosed to the subject via the informed consent process. Since this is an elective procedure and the subjects are volunteers, it can be assumed that their signature on the Informed Consent document indicates that the subject acknowledges and accepts the risks involved in the treatment of neck and chest rhytides.

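### The topical retinoid exclusion names the neck and chest, but the trial treats and scores only the face

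*Protocol*

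**What the plan says.** Under Selection Criteria, the exclusion list contains the line "Topical retinoid therapy on neck and/or chest within one month of study entry". No other criterion mentions topical retinoids; the 24-month line names oral retinoids and photosensitising drugs.

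The rest of the protocol concerns the face. The Protocol Summary gives the purpose as evaluating the laser with "topical cysteamine cream for treatment of melasma on the face". The study population paragraph says "one side of the face will be randomly selected for treatment with laser". The mMASI table adds scores from the forehead, the two malar areas and the chin.

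Three other places bear on facial retinoid use:

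- Selection Criteria also excludes a "history of surgical or cosmetic treatment, including prior skin lightening agents" where it was applied "to the planned treatment areas in the prior six weeks".
- Background lists, among the mainstays of melasma treatment, "topical skin-lightening and brightening agents such as hydroquinone, tranexamic acid, retinoids".
- The Visit 1 procedures include "Review past and current medications and skin care products".

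**The concern.** An eligibility rule should keep out treatments that act on the outcome at the site being measured. By the protocol's own Background, a retinoid on the face is an active treatment for melasma. Yet the one rule written for topical retinoids restricts them where nothing is treated or measured, and does not mention the face.

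Two things follow. Patients who use a retinoid on the neck or chest are refused although the trial has no evident need to refuse them, in a study of about 20 people. A patient using one on the face for a medical reason might be admitted by one screener and refused by another.

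If such a patient enters, the change from baseline is open to distortion in either direction. Continuing the retinoid could overstate improvement, and stopping it at entry could understate it. Any retinoid irritation would be recorded together with reactions to cysteamine and the laser.

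**Working it through.** The protocol states no figure on this point, so there is none to reproduce. The check is mainly a comparison of text, followed by simple arithmetic on assumed inputs.

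**Site of the rule against site of the trial.** The rule covers the neck and/or chest. Entry requires visible facial melasma (Selection Criteria), the laser goes to one side of the face (Study population, Laser Parameters), the imaging is facial (Photographs), and the mMASI sums four facial areas. Nothing in the trial treats or scores the neck or chest.

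**Likely origin.** Risk Management says that by signing consent the subject "accepts the risks involved in the treatment of neck and chest rhytides". A section headed for wrinkle classification actually grades melasma severity, and Clinical Evaluations retains a fine-wrinkle scale. Carry-over from another protocol is the simplest explanation.

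**Do other criteria cover facial use?**

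1. *Retinoid used to lighten the skin.* The six-week rule on lightening agents, read with the Background list, probably excludes it.
2. *Retinoid used for a medical reason, such as acne.* The six-week rule speaks of surgical or cosmetic treatment and mentions lightening agents as an instance. Medical use fits neither description plainly.
3. *The 24-month line.* Its retinoid wording is limited to oral drugs. Photosensitising drugs could be stretched to include topical retinoids, but a screener would naturally follow the line written specifically for them.
4. *Visit 1 review.* This would bring the use to light, but no decision rule is attached to it.

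The remaining gap is therefore medical use on the face.

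**Size.** From Sample Size Calculation: n = 20, or up to 25 with allowance for dropout. One patient is 1/20 = 5%, or 1/25 = 4%.

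If k patients each have their own mMASI change shifted by d points, the mean before-after change shifts by k × d / n. The values k = 1 to 2 and d = 1 to 3 are assumptions, not protocol figures.

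| n | Smallest shift | Largest shift |
|---|---|---|
| 20 | 1 × 1 / 20 = 0.05 | 2 × 3 / 20 = 0.30 |
| 25 | 1 × 1 / 25 = 0.04 | 2 × 3 / 25 = 0.24 |

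The largest value is 0.30 / 24 = 1.25% of the scale range, and the sign may be either. If both sides of the face are exposed alike and the shift is the same on each, it cancels in the between-side difference, which moves by about zero.

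**The case against.** The strongest reply is that facial retinoids are already excluded. The six-week rule names a class of agent, the Background places retinoids in that class, and the reason for use need not matter. On that reading facial users face a longer window than neck or chest users. The Visit 1 review makes an undetected user unlikely, and the primary objective is a between-side contrast that like exposure leaves almost untouched. The numerical effect rests wholly on assumed inputs. The line could then be treated as an editorial leftover, to be corrected together with the other wrinkle text.

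Much of this stands. The cover is substantial, the between-side contrast is safe to a good approximation, and the arithmetic only illustrates scale. Two points remain. First, the reading that closes the gap is possible but not the only one, and a specific retinoid line limited to another site invites the opposite reading. This is a rule that staff must apply, so ambiguity in it matters more than a stray heading. Second, before-after change is not incidental here. Study Design specifies a before-after analysis, the stated null hypothesis concerns improvement under the combination, and the clinical endpoints include mMASI change from baseline.

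The complaint that no reason is given for refusing neck or chest users carries limited weight alone, since few of the exclusions come with a rationale. It counts here because the site lies outside the trial altogether.

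**Conclusion.** The concern holds as a minor one. The criterion names the wrong body site, most probably through carry-over, and it leaves medical retinoid use on the face unclear. The protocol does not say how common such use is. Under the stated assumptions the mean before-after mMASI change would move by no more than 0.30 points with 20 patients, or 0.24 with 25. The near-zero effect on the between-side comparison assumes that the retinoid is used alike on both sides and acts alike on each. The effect on the irritation record cannot be quantified from the document. None of this threatens the trial's main comparison; the correction is worth making because it costs almost nothing.

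**What to change.** Replace the line with: *Topical retinoid therapy, for any indication, on the face (planned treatment area) within six weeks of study entry.* This names the treated site, settles medical use, and aligns the window with the existing six-week rule for the treatment areas. It also removes the neck and chest restriction.

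The cost is one line in the exclusion criteria. A few facial retinoid users would have to wait six weeks or would not be enrolled, while neck and chest users become eligible. The neck and chest wording in Risk Management can be corrected in the same amendment.
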